8.1. Primary Efficacy Endpoint

The primary endpoint will be calculated from standardized endogenous creatinine clearance measurements on Day 1 (first measurement after treatment) to Day 7, inclusive. Standardized endogenous creatinine clearance is assessed on each day during a 6 ± 1 hour period and calculated in mL/min as the mean creatinine clearance over the period, which is expected to be representative of the full 24 hours for that day.

An adjudication committee will review the standardized endogenous creatinine clearance data on a case-by-case basis to determine the values to be used in the analysis and for the derivation of AUC_{1-7} (see [Section 8.1.2](#)). The standardized endogenous creatinine clearance (mL/min) will be calculated by PPD Biostatistics using the following formula.

$$\frac{\text{Urine Creatinine (mg/dL)}}{\text{Serum Creatinine (mg/dL)}} \times \frac{\text{Total urine volume collected (mL)}}{\text{Stop date/time} - \text{Start date/time of urine collection (min)}}$$

- The urine creatinine (mg/dL) and serum creatinine (mg/dL) assessed by the central laboratory will be used to determine the standardized endogenous creatinine clearance.
- Per protocol, two blood samples are collected to evaluate the serum creatinine, one at the beginning of the urine sample collection and the other at the end of the urine sample collection. The average of these two serum creatinine measurements will be used in the formula above to assess the standardized endogenous creatinine clearance. In case there is only one serum creatinine sample available, then the serum creatinine concentration from that one sample will be used in the formula.
- The number of minutes from the start date/time to the stop date/time of urine sample collection and the total urine volume (mL) will be derived from the Urine Volume eCRF page. If the urine volume is recorded as 0 mL, then the standardized creatinine clearance will be 0 mL/min and will not be set to missing. If the urine volume is not recorded as missing but the volume is less than 30mL/24 hrs, then the standardized creatinine clearance will be set to 1 mL/min.

The adjudicated Part 2 data will be used to determine the AUC_{1-7} (primary endpoint), while the adjudicated Part 1 data will be used in a sensitivity analysis of the primary endpoint (as described in section 8.1.4). All data will be listed.

The primary endpoint is the area under the time-corrected endogenous creatinine clearance curve from Day 1 to Day 7 (AUC_{1-7}).

AUC_{1-7} is calculated as the average of the standardized endogenous creatinine clearance values over the 7 days. Specifically, denoting C_i as the standardized endogenous creatinine clearance on Day i , AUC_{1-7} is defined as:

$$AUC_{1-7} = \frac{1}{7} \sum_{i=1}^7 C_i$$

Any missing C_i values will be handled by linear interpolation where possible, otherwise they will be imputed by last observation carried forward (LOCF). When there are no preceding post-baseline measurements to use, the baseline measurement from Day 0 (i.e., prior to treatment) will be carried forward. If it is not possible to impute the missing values (as there is no baseline result), the standardized endogenous creatinine clearance values will be averaged based on the days available (i.e. if baseline, Day 1 and Day 2 are missing, the sum of the values from Day 3 to Day 7 will be divided by 5 – as there is 5 available days with non-missing data after imputation).

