3.4. Dose Adjustment/Modifications

Infusion of the study drug may be temporarily interrupted or permanently discontinued for a variety of reasons, including an adverse event or equipment malfunction. Therefore, it is possible that the total study drug dose and volume planned for a patient may differ from the total dose and volume administered and any such patients will be identified on the study drug infusion listing (see [Section 7.2](#)).

4. General Statistical Considerations

Combined analysis of primary endpoint

As described in [Section 8.1.1](#), the primary efficacy endpoint for this study is analyzed at both the interim analysis (based on all patients recruited in Part 1 up to that point) and at the end of the study (using all patients recruited after conclusion of Part 1, i.e. during Part 2). Patients recruited whilst the interim analysis is performed will be handled as follows:

- Those recruited to the optimal dose or placebo will form part of the Part 2 populations.
- Those recruited to the other doses will not be included in any efficacy analysis (except one sensitivity analysis on the primary endpoint), but their safety data will be analyzed.

The results from each analysis are then combined using an inverse normal method. This combined analysis of patients from Parts 1 and 2 rests on the assumption that patients recruited in each part of the study will belong to the same overall patient population. To check this assumption, data related to the baseline characteristics and demographics (for the selected optimal dose and placebo groups) will be repeated for Part 1 and Part 2. If any notable differences are observed, then the combined analysis will need to be interpreted with caution and further exploratory analysis will need to be conducted to investigate the possible causes.

The assumption of a consistent treatment effect across Parts 1 and 2 will be investigated by repeating the primary and key secondary efficacy analyses (for the optimal recAP dose and placebo treatment groups) for Part 1 and Part 2. Again, any notable differences will lead to the associated combined analysis being interpreted with caution and further exploratory analyses conducted to investigate the possible causes.

Combined analysis of secondary and ‘other’ endpoints

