4.3.3.1. PP Day 1 – 7 Combined

The PP Day 1 – 7 Combined Set includes all patients who were randomly assigned to a study drug in either Part 1 or Part 2 of the study, had no significant protocol deviations (PDs) (e.g. non-adherence to inclusion/exclusion criteria with enrollment of the patient, or non-adherence to FDA regulations or ICH E6(R1) guidelines) and had complete data

(meaning no more than two missing day 1-7 creatinine clearance values) for the primary endpoint. The primary endpoint will be analyzed for the PP Day 1-7 Combined Set, with patients analyzed according to the treatment they received. See Section 10.2.2 of the protocol and the Significant Protocol Deviation Rules document for further information on the handling of PDs for this study. Significant PDs will be identified prior to study unblinding and summarized by the deviation categories specified above.

4.3.3.2. PP Day 1 – 7 Part 1

The PP Day 1 – 7 Part 1 Set includes all patients who were randomly assigned to a study drug prior to the conclusion of Part 1, excluding patients enrolled during the interim analysis on placebo and the selected optimal recAP dose group and are included in the ITT Part 1 Interim Set, had no significant protocol deviations (PDs) (e.g. non-adherence to inclusion/exclusion criteria with enrollment of the patient, or non-adherence to FDA regulations or ICH E6(R1) guidelines) and had complete data (meaning no more than two missing day 1-7 creatinine clearance values) for the primary endpoint. The primary endpoint will be analyzed for the PP Day 1-7 Part 1 Set, with patients analyzed according to the treatment they received. See Section 10.2.2 of the protocol and the Significant Protocol Deviation Rules document for further information on the handling of PDs for this study. Significant PDs will be identified prior to study unblinding and summarized by the deviation categories specified above.

4.3.3.3. PP Day 1–7 Part 2

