Results from the primary analysis for interim analysis at Part 1 and for Part 2 will include least square means for each treatment and the difference in least squares means between the treatment groups will also be presented along with the associated 95% CI. P-values will be presented for least square mean treatment differences. The one-sided p-value for the combined analysis will be presented with the sample sizes and one-sided p-values from the interim analysis at Part 1 and at Part 2.

Descriptive statistics for the primary endpoint and mean standardized endogenous creatinine clearance at Day 1 to Day 7 will also be presented in a summary table by

treatment. This will be presented for all four treatment groups for the ITT Combined, ITT part 1 Interim, PP Day 1-7 Part 1, and also for the optimal recAP dose and placebo treatment groups for the ITT Part 2 and PP Day 1-7 Part 2 Sets. Analysis on the PP Set will be used as a supplement to the ITT analysis. The ITT Part 1 Interim Set (for all four treatment groups) will also be produced to help check the assumption of the combined analysis that patients recruited in each part of the study belong to the same overall patient population.

The primary endpoint, AUC_{1-7} , and standardized endogenous creatinine clearance at Day 1 to Day 7 will be listed.

A time-course plot of standardized endogenous creatinine clearance with associated error bars on each day will be presented for the optimal recAP dose and placebo groups. This plot will be repeated three times using different selection criteria for the data based on data imputation and adjudication of creatinine clearance data:

- 1) Including only calculated values (i.e. no imputed values)
- 2) Including all (non-adjudicated) calculated and imputed values
- 3) Including only adjudicated calculated and imputed values

The combined ITT analysis primary endpoint summary and analysis will be repeated as a supportive sensitivity analysis, excluding patients who died before day 8, with SAS[®] output from Part 1 and Part 2 models included on the primary combined analysis output. Additionally, descriptive statistics for the primary endpoint and mean time-corrected endogenous creatinine clearance at Day 1 to Day 7 will be presented in a summary table for the ITT Combined Set by treatment group and subgroup category, defined in [Section 8.1.5](#).

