8.1.2. Adjudication Committee

An adjudication committee will review the standardized endogenous creatinine clearance data on a case-by-case basis for part 1 patients in the same way as for the part 2 data review to determine the values to be used in the analysis. The adjudication committee will be provided with a data listing of collection time of urine and blood creatinine, their results as well as the calculated standardized endogenous creatinine clearance (more details are included in the adjudication committee charter). Additionally the adjudication committee will be provided with a data listing of collection time or urine urea nitrogen, volume of urine and BUN as well as the calculated value for urea clearance. The adjudication committee will also be provided with patients figures for standardized creatinine clearance and urea clearance.

The adjudication committee will then indicate for each record if the standardized endogenous creatinine clearance is acceptable (i.e. can be used in the analysis) and provide

comments (if applicable). PPD Biostatistics will use the standardized endogenous creatinine clearance deemed acceptable by the adjudication committee to re-derive the AUC₁₋₇.

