8.1.4. Sensitivity Analyses

The interim analysis was conducted on non-adjudicated data, so will be repeated using only the data deemed acceptable by the adjudication committee, therefore a sensitivity analysis will be performed on the primary endpoint using adjudicated Part 1 data.

In order to investigate the effect of imputing the missing data with LOCF, a sensitivity analysis will be conducted on the primary efficacy endpoint. The ANOVA analysis will be performed as described in [Section 8.1.1](#) but excluding any patients that died prior to Day 8 of the study. The descriptive statistics for the primary endpoint will also be repeated for this sensitivity analysis.

In addition, the ANOVA analysis (as described in [Section 8.1.1](#)) will be repeated including as additional covariates the baseline serum creatinine results and the baseline APACHE II score for the ITT Combined Set for the optimal recAP dose and Placebo. If the analysis does not converge, APACHE score will be categorized into two categories (< 25, ≥25).

Finally, the area under the time-corrected endogenous creatinine clearance curve from Day 5 to Day 7 (AUC₅₋₇) will be derived and analyzed with an ANOVA as described in [Section 8.1.1](#) to determine if the AUC₅₋₇ is a predictor of treatment effect.

AUC₅₋₇ is calculated as the average of the standardized endogenous creatinine clearance values over the 3 days. Specifically, denoting C_i as the standardized endogenous creatinine clearance on Day i , AUC₅₋₇ is defined as:

$$AUC_{5-7} = \frac{1}{3} \sum_{k=5}^7 C_i$$

Any missing C_i values will be handled by linear interpolation where possible, otherwise they will be imputed by last observation carried forward (LOCF). When there are no preceding post-baseline measurements to use, the baseline measurement from Day 0 (i.e., prior to treatment) will be carried forward. If there are missing values the values imputed for deriving AUC_{1-7} will be used to derive AUC_{5-7} .

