8.1.5. Supportive Analysis for the Primary Efficacy Endpoint

Due to the high variability of the creatinine clearance, the change from baseline in serum creatinine at Day 7 will be analyzed using an ANOVA with baseline serum creatinine, treatment (optimal recAP dose and placebo) and site as explanatory variables. The analysis will be run on the ITT Combined Set. If there is more than one serum creatinine result collected at Day 7, the average at Day 7 will be used to derive the change from baseline.

Additionally the primary endpoint analysis will be repeated with the following variables as additional factors within the ANOVA model for the ITT Combined Set (for the optimal recAP dose and placebo):

- Baseline biomarkers for kidney function:
 - Fractional excretion of sodium (<1%, ≥1 % - ≤2%, >2%).
 - Fractional excretion of urea (<35%, ≥35%).
- Baseline AKIN stage (stage 1, stage 2 and stage 3).
- Microbial infection. The following are the five possible outcomes:
 1. Gram positive
 2. Gram negative
 3. Mix gram positive/gram negative
 4. Other (e.g. fungal)
 5. Unknown.

If a blood culture is available this is leading. (Note that if a staphylococcus epidermis is the outcome this is a contamination and should be ignored). If no blood culture is available, the culture from the site for which the patient was hospitalized (index indication) is leading e.g. patient hospitalized for lung infection, with positive sputum and positive urine culture: sputum is then leading.

- Baseline urinary biomarkers for proximal tubular cell damage:

- KIM-1 (<Q1, ≥Q1 - <Q2, ≥Q2 - <Q3, ≥Q3).
- IL-18 (<Q1, ≥Q1 - <Q2, ≥Q2 - <Q3, ≥Q3).
- GST-alpha (<Q1, ≥Q1 - <Q2, ≥Q2 - <Q3, ≥Q3).

For GST-alpha, two different kits were used in the testing of GST-alpha therefore quartiles will be calculated separately for each kit and then for each subject, their baseline value will be compared against the quartile for the kit that was used to assess their GST-alpha baseline result. The resulting assigned quartile categories will then be combined together for subgroup summaries regardless of which kit was used.

- Baseline biomarkers for systemic inflammation:
 - IL-6 (<Q1, ≥Q1 - <Q2, ≥Q2 - <Q3, ≥Q3).
 - CRP (<Q1, ≥Q1 - <Q2, ≥Q2 - <Q3, ≥Q3).
 - LBP (<Q1, ≥Q1 - <Q2, ≥Q2 - <Q3, ≥Q3).
- Baseline eGFR by CKD-EPI formula (<Q1, ≥Q1 - <Q2, ≥Q2 - <Q3, ≥Q3).
- Time from first diagnosis of SA-AKI to start of recAP treatment (0 to <6 hours, 6 to <12 hours, 12 to <18 hours, 18 to <24 hours, ≥24 hours).

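### SAP 8.1 keeps adjudicated Part 1 clearances out of everything but a sensitivity analysis, so pooled AUC1-7 outputs appear to mix unscreened Part 1 with screened Part 2 values, which matters most for the dropped doses

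*SAP*

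**What the plan says.** SAP 8.1 sets a different rule for each part. The primary AUC1-7 rests on screened values from Part 2, whereas screened values from Part 1 go elsewhere: "while the adjudicated Part 1 data will be used in a sensitivity analysis of the primary endpoint". SAP 8.1.4 agrees. It records that the interim analysis used non-adjudicated data and provides for a repeat on accepted values as a sensitivity analysis of the primary endpoint. The change history entry for 8.1 (version 1.4) also ties adjudicated Part 1 data to the sensitivity analysis.

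SAP 8.1.2 points the other way. The committee works "for part 1 patients in the same way as for the part 2 data review", its review settles which values enter the analysis, and AUC1-7 is re-derived from accepted values. Nothing there restricts this to Part 2.

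Several outputs use AUC1-7 across both parts without naming a data version:

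- SAP 8.1.1: descriptive statistics for all four arms on ITT Combined; each dose versus placebo on PP Day 1-7 Combined; all doses combined versus placebo.
- SAP 8.1.4: the model adding baseline serum creatinine and APACHE II, "for the ITT Combined Set for the optimal recAP dose and Placebo", and the AUC5-7 analysis.
- SAP 8.1.5: the models with baseline characteristics "as additional factors within the ANOVA model for the ITT Combined Set".

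Two kinds of output set the parts side by side. The ITT Part 1 Interim summary in 8.1.1 "will also be produced to help check the assumption of the combined analysis" that both parts sample one population. SAP Section 4 adds: "The assumption of a consistent treatment effect across Parts 1 and 2 will be investigated by repeating the primary and key secondary efficacy analyses".

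Where the SAP does name versions, it treats the difference as real: the 8.1.1 time-course plot is produced separately for non-adjudicated and adjudicated values.

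**The concern.** Adjudication removes clearance values judged unusable. If it is applied to one part only, a pooled AUC1-7 combines two measurement processes. That would be mere noise if every arm had the same mix, but the arms do not. SAP 4.3.2 removes from ITT Combined the patients recruited to dropped doses during the interim period, so those two arms consist only of patients in the interim analysis. On the plain reading of 8.1 their AUC1-7 is wholly unscreened, while most placebo patients are screened. Screening status is then tied to treatment arm in exactly the outputs that show dose response, and a primary objective is to determine the dose or doses for Phase 3.

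There is also a practical risk. Sections 8.1 and 8.1.2 can lead two programmers to different analysis datasets, and the choice might be settled only after results are known.

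**Working it through.** **Inputs.** SAP 4.1: n1 = 30 per arm, n2 = 85 per arm, SD 49 mL/min, placebo response 60, effective response 69.5 (difference 9.5), strong response 79 (difference 19), one-sided 2.5%. SAP 8.1.1: inverse-normal weights √(30/115) and √(85/115). The documents give no rejection rate, mean shift or change in SD from adjudication, so those are assumed below.

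**The plan's own figures.** The two-part design was simulated with best-dose selection, the futility rule, a closed test with Dunnett p1 and no site term (100,000 runs per power scenario, 400,000 under the null).

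| Low / medium / high response | Simulated power | SAP 4.1 |
|---|---|---|
| 60 / 79 / 79 | 81.4% | 79% to 86% |
| 69.5 / 79 / 79 | 79.3% | 79% to 86% |
| 79 / 79 / 79 | 85.5% | 79% to 86% |
| only high dose strong (3 scenarios) | 66.1% to 68.7% | 66% to 67% |
| no effect (type I error) | 2.50% | 2.4% |

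Agreement is within 2 points for power. For type I error it is about 1.4 Monte Carlo standard errors of the plan's 50,000 runs (standard error 0.07 points).

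**Share of unscreened patients at planned sizes, plain reading of 8.1.**

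- Placebo and selected dose: 30/115 = 26.1% each.
- Each dropped dose: 30/30 = 100%.
- All doses combined: (30 + 30 + 30)/(115 + 30 + 30) = 90/175 = 51.4%.

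**Artefact in a difference.** Let d be the mean unscreened AUC1-7 minus the mean screened AUC1-7, the same in every arm and of either sign. Each arm's pooled mean moves by its unscreened share times d. A comparison therefore moves by the difference in shares times d:

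- Selected dose versus placebo: (0.261 − 0.261)d = 0.
- Dropped dose versus placebo: (1 − 0.261)d = 0.739d.
- All doses versus placebo: (0.514 − 0.261)d = 0.253d.

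| Assumed size of d (mL/min) | Dropped dose vs placebo | All doses vs placebo |
|---|---|---|
| 2 | 1.5 | 0.5 |
| 5 | 3.7 | 1.3 |
| 10 | 7.4 | 2.5 |

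For scale, the plan's effective difference is 9.5 mL/min.

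**Cross-part comparisons.** The level of AUC1-7 in Part 1 against Part 2 (descriptive, 8.1.1) moves by the full d. The treatment difference within each part (Section 4 check) moves by d − d = 0.

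**Extra variance, selected dose versus placebo, 115 per arm, difference 19.** Pooled variance = 0.261 × s1² + 0.739 × 49², where s1 is an assumed SD for unscreened Part 1 values.

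| s1 | Pooled SD | Power |
|---|---|---|
| 49 | 49.0 | 83.7% |
| 55 | 50.6 | 81.2% |
| 60 | 52.1 | 79.0% |
| 70 | 55.3 | 74.1% |

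**Combination test.** With s1 of 49 to 70 in Part 1 and 49 in Part 2, simulated type I error stayed at about 2.5%.

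**The case against.** The strongest reply is that the SAP never says the pooled tables mix data versions. That stands: it is an inference from 8.1, and 8.1.2 can be read as putting accepted values from both parts into the analysis. What is shown is a conflict between two sections, in which the more specific one leads to mixing.

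The plan also covers part of the ground already. The repeated interim ANOVA in 8.1.4 gives an adjudicated Part 1 comparison of all three doses with concurrent placebo, and the third version of the time-course plot uses adjudicated values only. Both deserve credit. Neither reaches the pooled four-arm summary, the PP Combined comparisons or the covariate and factor models.

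Three stronger readings are tempting and are not supported.

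- A reader might infer that the confirmatory test is compromised because an unscreened p1 meets a screened p2. Each p-value comes from its own part, with one rule for all arms in that part, and p1 is the result on which the dose was selected. Keeping it is defensible.
- A reader might infer that the Section 4 check of a consistent treatment effect is distorted. A uniform shift cancels within each part. The baseline comparison in that section does not use AUC1-7 at all.
- A reader might infer that PP completeness differs by part, given the limit "meaning no more than two missing day 1-7 creatinine clearance values". The SAP does not say whether a rejected value counts as missing in either part, so this is a gap and not a stated asymmetry.

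Finally, the factor and subgroup analyses are exploratory and PP is supplementary. That limits the consequences but does not justify tying data processing to arm.

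**Conclusion.** The concern holds as a conflict between SAP 8.1 and 8.1.2 whose plain reading mixes unscreened Part 1 with screened Part 2 values in pooled AUC1-7 outputs. It is worth correcting, but it does not threaten the confirmatory result.

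The bias risk is confined to outputs that involve dropped doses: about 0.74d for a dropped dose versus placebo and 0.25d for all doses versus placebo. The coefficients follow from planned group sizes and would change with the actual counts, particularly in the PP sets. The size and sign of d are unknown. If errors in rejected values balance out, d could be near zero. The 2 to 10 mL/min range is an assumption, as is a shift equal across arms.

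For selected dose versus placebo the cost is some added variance and no bias under a uniform shift. The descriptive comparison of AUC1-7 levels between parts is affected by the full d.

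**What to change.** Reconcile SAP 8.1 with 8.1.2 by naming the data version for each output:

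- **Non-adjudicated interim data:** p1, with its least squares means and confidence intervals, for the confirmatory combination test and the table that reports it.
- **Adjudicated values from both parts:** every other pooled or cross-part AUC1-7 and daily clearance output. These are the ITT Combined summaries, the PP Combined each-dose and all-doses comparisons, the 8.1.4 covariate model and AUC5-7, the 8.1.5 factor models, and the Part 1 versus Part 2 comparisons. Time-course plots that already name another version stay as they are.
- **PP completeness:** state that a rejected value counts as missing in both parts.

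The cost is a short SAP edit and a data flag, since the Part 1 review is already planned. There is one small downside: the covariate and factor models would then use a different Part 1 data version from the confirmatory test, so a change in the estimate could come from the covariates or from the data. Showing the unadjusted model on the adjudicated data as a reference separates the two.
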